6.3.5.9 Other Grade 3 or 4 Non-hematologic toxicities

Hold all treatment until toxicities resolve to < Grade 2. Upon resolution resume treatment and decrease irinotecan one dose level. If toxicities do not resolve within three weeks, subject shall be removed from study

6.3.5.10 Other

Any other dose modifications in study treatment that are not described above may be performed at the discretion of the treating investigator, provided that criteria for subject withdrawal from study treatment have not been met.

6.3.5.11 For treatment modification questions, please contact [name] at [contact] or email at: [contact].

6.3.6 MISSED DOSES

Missed doses will not be replaced during a cycle.

6.3.7 CHANGES IN BODY SURFACE AREA (BSA)

Dose adjustments for carfilzomib or irinotecan do not need to be made for weight gains/losses of $\leq 10\%$. Subjects with a Body Surface Area (BSA) of greater than 2.2 m² will receive a capped dose of carfilzomib based upon a 2.2 m² BSA. Subjects with BSA greater than 2.2 m² will receive the prescribed dose of irinotecan without a cap.

6.4 SAFETY CONSIDERATIONS

Based upon the experience in the Phase 1 and 2 clinical studies with carfilzomib, in approximately 700 subjects, the following observations are noted:

- A "first dose effect" has been seen, which is notable for fever, chills, rigors, and/or dyspnea occurring during the evening following the first day of infusion and an increase in creatinine on Day 2, which may be the clinical sequellae of rapid tumor lysis and/or cytokine release.
- Should a "first dose" effect occur at any point during Cycle 1 or 2, treatment with high dose glucocorticoids (e.g. methylprednisolone 50–100 mg) is recommended. In addition, intravenous fluids, vasopressors, oxygen, bronchodilators, and acetaminophen should be available for immediate use and instituted, as medically indicated.
- Dexamethasone 8 mg PO/IV will be administered prior to all carfilzomib doses during the first cycle and after that as per section 6.5.1. Subjects with active or suspected infection of any kind that required systemic treatment should not be dosed with carfilzomib until the infection has resolved and if being treated with anti-infective, the course of antibiotics has been completed.
- Subjects should have anemia corrected in accordance with the Institutional guidelines.

Carfilzomib and Irinotecan treatment can cause nausea, vomiting, diarrhea, or constipation sometimes requiring the use of antiemetics or antidiarrheals. Fluid and electrolyte replacement should be administered to prevent dehydration. Subjects should be advised about diarrhea caused by Irinotecan and should have loperamide readily available at home.

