6.3 DOSE REDUCTIONS/ADJUSTMENTS

6.3.1 DOSE LEVELS

Carfilzomib – Phase I portion of the study

Starting Dose	Dose Level -1	Dose Level -2
$20/27 mg/m^2$	$20/20 mg/m^2$	Hold
$20/36 mg/m^2$	$20/27 mg/m^2$	$20/20 mg/m^2$
$20/45 mg/m^2$	$20/36 mg/m^2$	$20/27 mg/m^2$
20/56 mg/m2	$20/45 mg/m^2$	$20/36 mg/m^2$
20/70 mg/m2	$20/56 mg/m^2$	$20/45 mg/m^2$

Carfilzomib – Phase II portion of the study

Starting Dose	Dose Level -1	Dose Level -2
20/36 mg/m ²	20/27 mg/m ²	20/20 mg/m ²

* Cycle 1 Day 1 & Day 2 doses are 20 mg/m2. All subsequent days as specified, i.e. 20/27 mg/m2 means Cycle 1 Day 1 & Day 2 doses are 20 mg/m2 and all other days are 27mg/m2.

In the event that carfilzomib is held on Day 2, 8, 9, 15 and/or 16 of therapy, missed doses are not to be made up. All dose reductions are permanent and no dose re-escalation will be allowed on this trial.

Irinotecan- Phase I and II portions of the study

Starting Dose	Dose Level -1	Dose Level -2
125 mg/m2	100 mg/m ²	75 mg/m ²

*If Dose level -1 is utilized

In the event that irinotecan is held on Day 8 and/or Day 15, missed doses are not to be made up. All dose reductions are permanent and no dose re-escalation will be allowed on this trial.

6.3.2 DOSE REDUCTIONS FOR CARFILZOMIB AND IRINOTECAN HEMATOLOGIC TOXICITIES:

The following table outlines the dose reduction guidelines for carfilzomib and irinotecan for thrombocytopenia and neutropenia that occurs at any point during the prior cycle:

Event Name	Neutropenia			
Grade of Event	Recommended Action for Carfilzomib	Recommended Action for Irinotecan		
≤ Grade 1	No change in dose	No change in dose		
Grade 2	No change in dose	No change in dose		
Grade 3	No change in dose	Hold [*] until \leq Grade 2. Resume at one dose level lower, if indicated. ^{**}		
Grade 4	Hold [*] until \leq Grade 2. Resume at one dose level lower, if indicated. ^{**}	Hold [*] until \leq Grade 2. Resume at one dose level lower, if indicated. ^{**}		
*Subjects requiring a delay of >3 weeks should go off protocol therapy.				
**Subjects requiring > two dose reductions should go off protocol therapy.				
No prophylactic growth factor support is allowed in cycle 1, but growth factor support in the				
event of neutropenia is encouraged and should be administered at the discretion of the				
treating physician and per National Comprehensive Cancer Network Guidelines				
(http://www.nccn.org).				

Event Name	Thrombocytopenia	

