6.3.3 DOSE REDUCTIONS OF CARFILZOMIB AND IRINOTECAN FOR NON-HEMATOLOGIC TOXICITIES

Dose adjustment guidelines for non-hematologic toxicities that occur at any point during the prior cycle are summarized as follows:

Event name	Recommended Action	Recommended Action
Grade of Event	Carfilzomib	Irinotecan
Allergic reaction/hypersensitivity		
Grade 2 – 3	Hold until ≤ Grade 1, reinstitute at full dose.	No change in dose
Grade 4	Discontinue	No change in dose
Tumor lysis syndrome $(\geq 3 \text{ of following:} \geq 50\% \text{ increase in creatinine, uric acid, or phosphate;} \geq 30\% \text{ increase in potassium;} \geq 20\% \text{ decrease in calcium; or } \geq 2-\text{fold increase in LDH}$	Hold carfilzomib until all abnormalities in serum chemistries have resolved. Reinstitute at full doses.	Hold irinotecan until all abnormalities in serum chemistries have resolved. Reinstitute at full doses.
Infection Grade 3 or 4	Hold carfilzomib until systemic treatment for infection complete. If no neutropenia, restart at full dose. If neutropenic, follow neutropenic instructions.	Hold irinotecan until systemic treatment for infection complete. If no neutropenia, restart at full dose. If neutropenic, follow neutropenic instructions.
Peripheral Neuropathy Grade 2 treatment emergent with pain or Grade 3neuropathy	Continue to dose. If neuropathy persists for more than two weeks hold carfilzomib until resolved to ≤ Gr 2 without pain. Then restart at 1 dose decrement if indicated.**	No change in dose
Peripheral Neuropathy Grade 4 neuropathy	Discontinue	Discontinue
Serum creatinine elevation Grade 2, 3 or 4	Hold until ≤ Grade 1. Resume at one dose level lower, if indicated.**	Hold until ≤ Grade 1. Resume at one dose level lower, if indicated.**

Hepatic Impairment Grade 3 or 4 elevation of transaminases or bilirubin	Hold Carfilzomib until < Grade 2. Resume at one dose level lower, if indicated.**	Hold Irinotecan until < Grade 2. Resume at one dose level lower, if indicated.**
Congestive heart failure Grade 3 or 4	Any subject with symptoms of grade 3 or 4 congestive heart failure, whether or not drug related, must have the dose held until resolution to grade 2 or less, or return to baseline, after which treatment may continue at 1 dose decrement, or the subject may be withdrawn from the study. If no resolution after 2 weeks, the subject will be withdrawn from the study.	No change in dose

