6.3.5.2 Infections

Subjects with grade 3 or 4 active or suspected infections should have treatment withheld until infection has resolved and anti-infective treatment has been completed. After the infection has resolved and anti-infective treatment has been completed, treatment may continue at the original dose. If there is no resolution of toxicity after 3 weeks, the subject will be withdrawn from the study.

6.3.5.3 Congestive Heart Failure (CHF)

Any subject with symptoms of grade 3 or 4 CHF or any other suspected acute cardiac event, whether or not drug related, must have the dose held until resolution. After the event has resolved or returned to baseline, treatment may continue at 1 dose decrement, with the approval of the Medical Monitor, or the subject may be withdrawn from the study. If there is no resolution of CHF after 2 weeks, the subject will be withdrawn from the study.

6.3.5.4 Pulmonary Hypertension

Pulmonary arterial hypertension was reported in 2% of patients treated with carfilzomib and was Grade 3 or greater in less than 1% of patients. Evaluate with cardiac imaging and/or other tests as indicated. Unless otherwise specified in the individual protocol, withhold carfilzomib for pulmonary hypertension until resolved or returned to baseline and consider whether to restart carfilzomib based on a benefit/risk assessment.

6.3.5.5 Myocardial Infarction

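### Sections 6.3.3, 6.3.5.2 and 6.4 give infection rules that differ on release, restart dose and trigger, and nothing says which governs

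*Combined protocol and SAP*

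**What the plan says.** Three sections of the protocol instruct sites on infection.

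- **Section 6.3.3 (table of non-hematologic toxicities).** The row is labelled "Infection Grade 3 or 4". For carfilzomib it reads "Hold carfilzomib until systemic treatment for infection complete. If no neutropenia, restart at full dose. If neutropenic, follow neutropenic instructions", and the irinotecan column has the matching instruction.
- **Section 6.3.5.2.** "Subjects with grade 3 or 4 active or suspected infections should have treatment withheld until infection has resolved and anti-infective treatment has been completed". It then adds: "After the infection has resolved and anti-infective treatment has been completed, treatment may continue at the original dose".
- **Section 6.4.** "Subjects with active or suspected infection of any kind that required systemic treatment should not be dosed with carfilzomib until the infection has resolved". The sentence goes on to require that any anti-infective course be finished. It sets no grade threshold, names carfilzomib only and gives no restart dose.

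The 6.3.3 row points to the neutropenia table in Section 6.3.2. At Grade 4 that table holds both drugs and then says "Resume at one dose level lower, if indicated" for each. At Grade 3 it leaves carfilzomib unchanged and holds irinotecan, with the same wording for its restart. Under Section 6.3.1, held doses are not made up and reductions are permanent. Section 6.3.6 repeats that missed doses are not replaced.

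**The concern.** A site treating an infected subject needs four answers: whether to hold, which drug to hold, when to release, and at what dose to restart. The three sections answer these differently or not at all, and none is said to take precedence.

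The situation will not be rare. Section 9.3.1 lists respiratory tract infection and pneumonia as very common with carfilzomib (more than 1 in 10), and Section 9.3.2 lists infection among effects seen in more than 20% of subjects on irinotecan. At least 8 sites will read the text independently (Section 3.2), in a single-arm phase II with 40 evaluable subjects per stratum (Section 11).

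Because lost doses stay lost and reductions cannot be reversed, the choice of section can alter what a subject receives. More than two reductions also takes a subject off protocol therapy, so a reduction made under one reading and not another counts towards that limit. The stakes are consistency of delivered dose between sites and the risk of dosing while an infection is still active.

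**Working it through.** The plan states no figure on this point, so there is none to reproduce. The check sets the texts side by side and then sizes the one difference that can be counted.

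**Step 1. Comparison**

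| | 6.3.3 | 6.3.5.2 | 6.4 |
|---|---|---|---|
| Trigger | Grade 3 or 4 | Grade 3 or 4, active or suspected | Any infection needing systemic treatment |
| Drug held | Both | Treatment, unspecified | Carfilzomib |
| Release | Systemic treatment complete | Resolved and anti-infectives complete | Resolved and anti-infectives complete |
| Restart dose | Full if not neutropenic; otherwise neutropenia table | Original | Not stated |

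**Step 2. Release.** Take a Grade 3 infection whose anti-infective course has ended but which has not resolved. Section 6.3.3 permits restart; 6.3.5.2 and 6.4 do not. This is a direct difference for the same event.

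**Step 3. Restart dose.** Take a Grade 3 or 4 infection with neutropenia.

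- Grade 4 neutropenia: the 6.3.3 route leads to one level lower, if indicated, for both drugs. From Section 6.3.1, carfilzomib goes from 36 to 27 mg/m² (27/36 = 0.75, 25% lower) and irinotecan from 125 to 100 mg/m² (100/125 = 0.80, 20% lower). Read alone, 6.3.5.2 allows 36 and 125.
- Grade 3 neutropenia: carfilzomib is the same on both routes. Only irinotecan could differ.
- Grade 2 or lower: no difference, because the neutropenia table changes nothing.

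**Step 4. Trigger.** Take an infection below Grade 3 given a systemic anti-infective. Section 6.4 holds carfilzomib. Sections 6.3.3 and 6.3.5.2 say nothing, so a site using only those sections would not hold it. Section 6.4 does not say what happens to irinotecan.

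Carfilzomib is scheduled on Days 1, 2, 8, 9, 15 and 16. The documents give no anti-infective course length, so length L is an assumption. For a course starting on Day s (s = 2 to 16):

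doses lost = number of scheduled days d with s ≤ d ≤ s + L − 1.

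This assumes that the infection has resolved by the end of the course and that dosing resumes the next day. Only doses in the same cycle are counted.

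| Assumed course | Doses lost under 6.4, range over start days |
|---|---|
| 5 days | 0 to 2 |
| 7 days | 1 to 2 |
| 10 days | 1 to 4 |
| 14 days | 1 to 4 |

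A 5-day course from Day 3 covers Days 3 to 7 and costs nothing. A 10-day course from Day 7 covers Days 7 to 16 and costs Days 8, 9, 15 and 16. The shortest course that can cost four doses is 9 days, starting on Day 8. A 10-day course costs four only if it starts on Day 7 or 8; a 14-day course does so from any of Days 2 to 8.

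At the maximum of four doses, 4 × 36 = 144 mg/m² is lost. That is 67% of 6 × 36 = 216 mg/m² in Cycle 2 or later, or 78% of 2 × 20 + 4 × 36 = 184 mg/m² in Cycle 1.

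**The case against.** The strongest reply is that the sections can mostly be read together.

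- **Trigger.** Sections 6.3.3 and 6.3.5.2 do not tell sites to keep dosing below Grade 3. Where the protocol wants dosing to continue it says so: the cytopenia tables print an explicit no-change entry at lower grades, and Section 6.3.5.8 lists conditions that need no carfilzomib hold. Low-grade infection appears in neither, and 6.4 is explicit. A site that follows 6.4 satisfies all three triggers. This stands: it is a gap in the dose-modification sections, not an instruction to dose.
- **Restart dose.** Section 6.3.2 covers neutropenia at any point in the prior cycle, with or without infection, and nothing in 6.3.5.2 switches it off. Section 6.3.5.2 is permissive, and the table reduces only if indicated. This largely stands. A reader might infer that 6.3.5.2 returns a subject with Grade 4 neutropenia to 36 and 125 mg/m² regardless. The documents do not support that, because 6.3.2 arguably still applies in its own right. What remains is that one infection text carries the neutropenia cross-reference and the other omits it.
- **Release.** Applying the stricter condition meets all three texts. That is true, but nothing tells a site to do so.
- **Drug.** A carfilzomib precaution in a list of carfilzomib experience does not contradict a rule covering both drugs. This is fair; the issue is silence on irinotecan below Grade 3.
- **Recourse.** Section 6.3.5.11 gives a contact for treatment-modification questions. That helps sites that notice the discrepancy, but it is not a precedence rule.

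**Conclusion.** The three infection texts do not agree as written and should be reconciled. The clearest difference is release: treatment complete in 6.3.3, against resolved and complete in 6.3.5.2 and 6.4. The restart-dose difference is narrower: carfilzomib could be affected only with Grade 4 neutropenia, irinotecan at Grade 3 or 4, and only if 6.3.2 is not applied independently. The trigger difference is between an explicit bar in 6.4 and silence in the dose-modification sections.

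A reader might infer that the protocol lets the same infection cost four carfilzomib doses or none. That is too strong as a general statement. The figure of none depends on a site overlooking 6.4. The figure of four needs an assumed course of at least 9 days at the right point in the cycle; a course of 7 days or less costs at most two.

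The documents do not show how often the divergent cases would arise, so no effect on the trial's conclusions can be calculated. The consequence is possible variation in delivered dose and in the risk of dosing during infection. Alpha, power and the six-month survival decision rule are not involved.

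**What to change.** Reconcile Sections 6.3.3, 6.3.5.2 and 6.4, together with the neutropenia table in 6.3.2, into one infection rule. Put it in one place, such as the 6.3.3 row, and have the other sections refer to it. The rule should state:

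1. the grade or treatment that triggers a hold;
2. the condition that ends the hold;
3. which drug or drugs are held, including irinotecan below Grade 3;
4. how an infection with neutropenia is handled, and whether 6.3.2 applies.

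The clinical content is for the sponsor to choose; none is proposed here. The cost is amendment wording and notification of sites, with no added visits, tests or subjects.

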6.5 CONCOMITANT MEDICATIONS

Concomitant medication is defined as any prescription or over-the-counter preparation including vitamins and supplements. Concomitant medications should be recorded from 14 days before Day 1 through the end of the subject's study participation. Any change in concomitant medications must be recorded.

6.5.1 REQUIRED CONCOMITANT MEDICATIONS

Female subjects of child-bearing potential must agree to use dual methods of contraception for the duration of the study. Male subjects must agree to use a barrier method of contraception for the duration of the study if sexually active with a female of child-bearing potential.

Dexamethasone 8 mg PO/IV will be administered prior to all carfilzomib doses during the first cycle.. A higher dose of dexamethasone may be used per institutional standard. If treatment-related fever, rigors, chills, and/or dyspnea are observed following any dose of carfilzomib after dexamethasone has been discontinued, the subject should receive treatment for infusion reaction per the investigator's institutional standard and dexamethasone (8 mg PO/IV) should be re-instituted and administered prior to all subsequent doses.

All subjects must receive prophylaxis with hydration (see Section 6.1).

6.5.2 OPTIONAL AND ALLOWED CONCOMITANT MEDICATIONS

Subjects may receive RBC or platelet transfusions if clinically indicated in accordance with institutional guidelines. FDA approved bisphosphonates are allowed. Subjects may receive antiemetics and antidiarrheals as necessary, but these should not be administered unless indicated. Colony-stimulating factors may be used if neutropenia occurs but should not be given prophylactically in cycle 1 of therapy.

Vitamins and supplements should be recorded on the concomitant medication page. All transfusions and/or blood product related procedures must be recorded on the appropriate form.

6.5.3 EXCLUDED CONCOMITANT MEDICATIONS

Concurrent therapy with other investigative anticancer therapies or other investigational agents is not allowed.

7 STUDY TESTS AND OBSERVATIONS:

Phase Ib Study Calendar:

Required Studies		Cycle 1			Cycle 2,4,6					Cycle 3, 5												
-		Day			Day																	
	Screen within 2weeks unless specified	1	2	8	9	15	16	1	2	8	9	15	16	22	1	2	8	9	15	16	Off study	Follow-up [@]
PHYSICAL																						
Informed Consent	X																					
Medical History	X																					
Physical Examination	X							X							X						X	X
Performance Status and Weight	X							X							X						X	X
Toxicity Assessment								X							X						X	X
Disease Assessment	X							X							X							
RADIOLOGY																						
CT/MRI scan ¶	X													X							X	X
Brain CT/MRI #	Х																					
ECG#	Х																					
LABORATORY																						
CBC w/differential	X*	X		X		Х		X		X		X			X		X		X		X	X
Serum chemistries §	X*	X		X		X		X		X		X			X		X		X		X	X
Serum Magnesium	X*	X						X							X						X	X
Serum or urine Pregnancy Test	X*																					
TREATMENT																						
Irinotecan √		X		X		X		X		X		X			X		X		X			
Carfilzomib $$ (study provided)		X	X	X	X	Х	X	X	X	X	X	X	X		X	X	X	X	X	X		
Dexamethasone 8 mg ⁺		X	X	X	X	X	X															
PD/Correlative																						
Pharmcodynamic blood tests £		X	X																			
Tissue Submission &	X			1														1				

¶ CT or MRI (the same method used at prestudy to meet the eligibility criteria in Section 5.3) must be repeated every8 weeks until disease progression. Once off study, the frequency of this scan may be reduced to every 3 months until disease progression.

#Prestudy, and then as clinically indicated

* This test is required prestudy within 2 weeks of starting study medication.

§ Sodium, potassium, calcium, chloride, creatinine, magnesium, SGOT, SGPT, alkaline phosphatase, total bilirubin prior to treatment on Day 1 of each cycle (at most 2 days prior to Day 1 of the next cycle); Sodium, potassium, chloride, creatinine, prior to treatment on Day 8 & 15

√ After completion of Cycle 6 and if the subject has not met criteria for disease progression, carfilzomib and irinotecan may be continued at the discretion of the sponsor and treating physician.

+ Dexamethasone 8 mg prior to all carfilzomib doses during the first cycle and after that as per section 6.5.1.

£ PD: Carfilzomib proteasome chymotrypsin-like activity in PBMC (LMP7 and b5 activity) and gamma-H2AX and Topoisomerase-I expression Day 1: The sampling times relative to the start of irinotecan infusion: Pre-irinotecan, 90 min, 2 hours, 5.5 hours; Day 2: pre-carfilzomib infusion

& Submit tumor block or 10 unstained slides of pre-existing tumor

@ Follow-up will be for 30 days after last treatment or until all drug-associated (possible, probably or definite) toxicities have resolved to Grade 1 or less

Phase II Study Calendar:

Required Studies		Cycle 1				Cycle 2,4,6					Cycle 3, 5											
-			Day Day																			
	Screen within 2 weeks unless specified	1	2	8	9	15	16	1	2	8	9	15	16	22	1	2	8	9	15	16	Off study	$Follow-up^{@}$
PHYSICAL																						
Informed Consent	X																					
Medical History	Х																					
Physical Examination	X							Х							Х						Х	Х
Performance Status and Weight	Х							Х							Х						Х	Х
Toxicity Assessment								Х							Х						Х	Х
Disease Assessment	X							Х							Х							
RADIOLOGY																						
CT/MRI scan ¶	Х													Х							Х	Х
Brain CT/MRI #	Х																					
ECG#	X																					
LABORATORY																						
CBC w/differential	X*	Х		Х		х		Х		Х		Х			Х		Х		Х		Х	Х
Serum chemistries §	X*	Х		Х		Х		Х		Х		Х			Х		Х		Х		Х	Х
Serum Magnesium	X*	Х						Х							Х						Х	Х
Serum or urine Pregnancy Test	X*																					
TREATMENT																						
Irinotecan √		Х		Х		Х		Х		Х		Х			Х		Х		Х			
Carfilzomib $$ (study provided)		Х	Х	Х	Х	х	Х	Х	Х	Х	х	Х	Х		Х	Х	Х	Х	Х	Х		
Dexamethasone 8 mg		Х	Х	Х	Х	Х	Х															
PK/PD/Correlative																						
Pharmcodynamic blood tests £		X	Х																			
Tissue Submission &	X			1				1		1					1			1				ĺ

¶ CT or MRI (the same method used at prestudy to meet the eligibility criteria in Section 5.3) must be repeated after ever two cycles of treatment until disease progression. Once off study, the frequency of this scan may be reduced to every 3 months until disease progression.

#Prestudy, and then as clinically indicated

* This test is required prestudy within 2 weeks of starting study medication.

§ Sodium, potassium, calcium, chloride, , creatinine, magnesium, SGOT, , alkaline phosphatase, total bilirubin prior to treatment on Day 1 of each cycle (at most 2 days prior to Day 1 of the next cycle); Sodium, potassium, chloride, creatinine, prior to treatment on Day 8 & 15

√ After completion of Cycle 6 and if the subject has not met criteria for disease progression, carfilzomib and irinotecan may be continued at the discretion of the investigator-sponsor and treating physician.

+ Dexamethasone 8 mg prior to all carfilzomib doses during the first cycle and after that as per section 6.5.1.

£ PD: In first 15 subjects in each stratum: Carfilzonib proteasome chymotrypsin-like activity in PBMC (LMP7 and b5 activity), Gamma-H2AX and Topoisomerase-I in PBMC Day 1: The sampling times relative to the start of irinotecan infusion: Pre-irinotecan, 90 min, 2 hours, 5.5 hours; Day 2: pre-carfilzonib infusion

& All subjects: Submit tumor block or 10 unstained slides of pre-existing tumor

@ Follow-up will be every 3 months for up to 2 years

8 STUDY DISCONTINUATION

8.1 CRITERIA FOR REMOVAL FROM PROTOCOL TREATMENT:

- a. Completion of 6 cycles of chemotherapy.
- b. Progression of disease or symptomatic deterioration (as defined in Appendix B-Section 2).
- c. Unacceptable toxicity.
- d. Treatment delay for any reason for greater than 3 weeks
- e. At the discretion of the treating physician
- f. The subject may withdraw from the study at any time for any reason.

Subjects will receive up to 6 cycles of therapy. Subjects who are deemed to be clinically benefitting from this therapy by the treating physician, may be considered for further treatment at the discretion of the sponsor, Amgen, the treating physician and the study PI.

ALL REASONS FOR DISCONTINUATION OF TREATMENT MUST BE DOCUMENTED IN THE OFF TREATMENT NOTICE ECRF

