6.2.3 DOSE ESCALATION SCHEME - FOR PHASE I ONLY

Dose escalation will proceed within each cohort according to the following scheme. Dose-limiting toxicities (DLT) are defined above.

Number of Subjects with DLT at a Given Dose Level	Escalation Decision Rule
0 out of 3	Enter 3 subjects at the next dose level.
> 2	Dose escalation will be stopped. This dose level will be declared the maximally administered dose (highest dose administered). Three (3) additional subjects will be entered at the next lowest dose level if only 3 subjects were treated previously at that dose.
1 out of 3	 Enter at least 3 more subjects at this dose level. a. If 0 of these 3 subjects experience DLT, proceed to the next dose level. b. If 1 or more of this group suffer DLT, then dose escalation is stopped, and this dose is declared the maximally administered dose. Three (3) additional subjects will be entered at the next lowest dose level if only 3 subjects were treated previously at that dose.
≤ 1 out of 6 at highest dose level below the maximally administered dose	This is generally the recommended phase II dose. At least 6 subjects must be entered at the recommended phase II dose.

6.2.4 PHASE II PORTION OF THE STUDY

AGENT	DOSE	ROUTE	DAYS	INTERVAL
Irinotecan	125 mg/m ²	IV infusion (over 90 min)	1, 8, 15	q 28 days
Carfilzomib	20/36 mg/m ²	IV infusion (over 30 min)	1, 2, 8, 9 15 and 16	q 28 days

* Cycle 1 Day 1 & Day 2 doses are 20 mg/m2. All subsequent days as specified, i.e. 20/27 mg/m2 means Cycle 1 Day 1 & Day 2 doses are 20 mg/m2 and all other days are 27mg/m2.

Additional cycles of therapy may be administered provided the subject meets all of the

following at the **beginning of each cycle**:

- ANC \geq 1,500/µL.
- Platelet count $\geq 100,000/\mu L$.
- All other Grade 2, 3 or 4 non-hematological toxicities have resolved as required in section 6.3.3.
- Serum creatinine $\leq 1.5 \text{ x}$ ULN OR measured or calculated creatinine clearance $\geq 60 \text{ mL/min}$ using the Cockcroft-Gault.

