11.3 PLANNED METHODS OF ANALYSIS

Six month survival and progression free survival rates, as well as response to treatment, will be calculated based on all subjects who receive the recommended Phase II dose of the drug combination. All eligible subjects accrued to phase II who have received at least one dose of each drug in the regimen will be considered as evaluable in the phase II analysis.

Survival will be estimated using the Kaplan-Meier method, separately for each stratum. Response and progression will be determined according to RECIST criteria. Overall survival is defined as the time between registration and death due to any cause. Subjects last known to be alive are censored at date of last contact. Progression free survival is defined as the date of registration to the date of first documentation of progression, or death due to any cause. Subjects last known to be alive and progression free are censored at the date of last contact. Due to the limited sample size in a Phase II setting, correlative studies will be considered exploratory in nature and will be used to formulate hypotheses that can be tested using correlative data from a Phase III setting.

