- 1 Restricted in physically strenuous activity but ambulatory and able to carry out work of a light or sedentary nature, e.g., light housework, office work.
- 2 Ambulatory and capable of self-care but unable to carry out any work activities; up and about more than 50% of waking hours.
- 3 Capable of limited self-care, confined to bed or chair more than 50% of waking hours.
- 4 Completely disabled; cannot carry on any self-care; totally confined to bed or chair.

5. **Progression-Free Survival** From the date of registration to first documentation of progression or symptomatic deterioration (as defined in 2.d and 2.e), or death due to any cause. Subjects last known to be alive and progression-free are censored at date of last contact.

6. **Overall Survival** From the date of registration to the date of death due to any cause. Subjects last known to be alive are censored at date of last contact.

7. Time to Treatment Failure From date of registration to date of first observation of progressive disease (as defined in 2.d), death due to any cause, symptomatic deterioration (as defined in 2.e), or early discontinuation of treatment.

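### Phase II scans follow treatment cycles rather than the calendar, so late cycle starts postpone detection of progression on average; the effect on PFS is modest and the primary endpoint is untouched.

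*Combined protocol and SAP*

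**What the plan says.** - **Scan timing, Phase II (Section 7, Phase II Study Calendar).** On-treatment CT/MRI "must be repeated after ever two cycles of treatment until disease progression". The grid marks it on Day 22 of Cycles 2, 4 and 6.
- **Scan timing, Phase Ib (same section).** The footnote says CT/MRI "must be repeated every8 weeks until disease progression". The Phase Ib grid nevertheless carries the same Day 22 entry for Cycles 2, 4 and 6.
- **After leaving study (Phase II footnote).** "Once off study, the frequency of this scan may be reduced to every 3 months until disease progression".
- **Cycle starts (Section 6.2.4).** Cycles are nominally 28 days. "Additional cycles of therapy may be administered provided the subject meets all of the" listed conditions: neutrophils, platelets, recovery from non-hematologic toxicity, and renal function.
- **Limit on delay (Section 8.1).** Removal from treatment follows "Treatment delay for any reason for greater than 3 weeks". No limit on cumulative delay is stated.
- **Doses missed within a cycle (Section 6.3.6).** "Missed doses will not be replaced during a cycle".
- **PFS (Section 11.3).** "Progression free survival is defined as the date of registration to the date of first documentation of progression, or death due to any cause". Appendix B, item 5, words it differently: "From the date of registration to first documentation of progression or symptomatic deterioration", or death.

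For Phase II on-treatment imaging the plan gives no scan window, no calendar backstop and no analysis rule for late scans.

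**The concern.** The 8-week rule and the two-cycle rule agree only while every cycle starts on time. When a cycle starts late because a subject has not recovered, the next scan moves with it. Progression on imaging is dated at the scan that shows it, so a toxicity-driven delay feeds into the PFS date.

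Delays are plausible here. Section 12.2.3 expects neutropenia and diarrhea to occur in this trial, and Sections 6.3.2 and 6.5.2 do not allow prophylactic growth factor in Cycle 1, so Cycle 2 could start late, before the first scan.

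PFS is a named Phase II secondary endpoint. With no control arm to share the distortion, it matters when PFS is read against outside data, or across the platinum-sensitive and platinum-refractory strata if their delays differ.

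**Working it through.** The plan states no PFS benchmark, power or threshold, so there is no figure of its own to reproduce. The check has two parts.

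**1. Scan dates from the plan's own rules.** Inputs: 28-day cycles (Section 6.2.4), scan on Day 22 of Cycles 2, 4 and 6 (Section 7 grid), at most 21 days per delay (Section 8.1). Cycle 1 Day 1 is day 1.

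Undelayed scan day = 28 x (cycle number - 1) + 22. Latest scan day adds 21 days for every cycle start before it.

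| Scan | Undelayed | Latest |
|---|---|---|
| Cycle 2 | 28 + 22 = 50 | 50 + 1 x 21 = 71 |
| Cycle 4 | 84 + 22 = 106 | 106 + 3 x 21 = 169 |
| Cycle 6 | 140 + 22 = 162 | 162 + 5 x 21 = 267 |

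The interval between scans is 56 days undelayed and at most 56 + 2 x 21 = 98 days (98/56 = 1.75). Only one cycle start precedes the first scan, so that scan can slip by 3 weeks and no more.

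**2. Effect on PFS, by simulation.** The same 400,000 simulated subjects were scanned under two schedules: cycle-tied, and fixed at weeks 7, 15 and 23. Both then used 13-week intervals. Assumptions not in the documents:

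- exponential true time to progression, median 8, 12 or 16 weeks;
- median survival after progression 13 weeks;
- 25%, 50% or 100% of cycle starts delayed, by a uniform 1 day up to 1, 2 or 3 weeks;
- every subject on the scan schedule through Cycle 6.

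Results in weeks. For cycle-tied scans the range covers the nine delay scenarios. Lag is the time from true progression to detection, for progressions in the first 23 weeks.

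| True median | Lag: calendar | Lag: cycle-tied | Mean PFS: calendar | Mean PFS: cycle-tied | Median PFS: calendar | Median PFS: cycle-tied |
|---|---|---|---|---|---|---|
| 8 | 4.14 | 4.30-5.66 | 15.47 | 15.54-16.28 | 14.0 | 9.0-13.6 |
| 12 | 4.05 | 4.23-5.64 | 21.47 | 21.52-22.12 | 15.0 | 15.4-18.6 |
| 16 | 4.01 | 4.20-5.63 | 27.37 | 27.41-27.91 | 21.7 | 17.4-20.4 |

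- **Lag** rises in every scenario, from 4.30 - 4.14 = 0.16 to 5.63 - 4.01 = 1.62 weeks.
- **Mean PFS** rises in every scenario, from 27.41 - 27.37 = 0.04 to 16.28 - 15.47 = 0.81 weeks.
- **Individual subjects:** 33-72% have a later PFS date and 3-32% an earlier one, because a postponed scan can catch a progression that an on-time scan would just have missed.
- **Median PFS** can move either way, for the same reason. With a true median of 8 weeks, 1 - 2^(-7/8) = 45% have progressed by a week-7 scan but 1 - 2^(-9/8) = 54% by a week-9 scan. The later scan catches more than half, so the median falls to about that date.

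**Hand check on lag.** Mean lag is roughly half the scan interval. If every start is late by 1 to 21 days (mean 11), two starts add 22 days to an interval and 11 days, or 1.6 weeks, to the lag. If 25% are late by 1 to 7 days (mean 4), two starts add 2 x 0.25 x 4 = 2 days and the lag grows by 1 day, or 0.14 weeks. Both are close to the simulated extremes.

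**The case against.** The strongest case against the point is that nothing in the plan turns on PFS. Section 11 tests six-month survival only (at least 22 of 40 alive in the sensitive stratum, 15 of 40 in the refractory stratum) and plans no formal PFS comparison. Nor can the reader tell whether outside PFS figures came from calendar or cycle-based scanning, so the net bias against them is unknown. This stands, and it keeps the point minor.

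Partial safeguards also stand. Disease assessment is scheduled on Day 1 of every cycle from Cycle 2, deaths count as events, there is an off-study scan, and Appendix B (though not Section 11.3) counts symptomatic deterioration. More than two dose reductions take a subject off therapy, so repeated maximal delays, and a third scan as late as day 267, should be uncommon.

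Three stronger readings are tempting but not supported:

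- **PFS is inflated by 11-23%.** A reader might take half of a 3- or 6-week delay (1.5 or 3 weeks) over the 13.3-week topotecan median time to progression quoted in Section 1.5. That describes a subject delayed by 3 or 6 weeks within the interval in which progression occurs. It is not an expected effect for the trial: the documents give no delay frequency, and 6 weeks cannot arise before the first scan.
- **Median PFS is biased upward, or every delayed subject is dated later.** The upward shift holds for the mean only.
- **Any dose delay moves the scans.** Doses missed within a cycle are not replaced, so only late cycle starts matter.

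The Phase Ib comparison is also imperfect. Its grid carries the same Day 22 entry, so its footnote and grid disagree as soon as a cycle is late.

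**Conclusion.** The point holds as a small design weakness. Phase II on-treatment imaging has no calendar anchor, so the timing of a named secondary endpoint depends partly on toxicity, and detection is later on average.

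The scan-date limits (day 71 for the first scan, 98 days for a later interval) follow directly from the plan. The average effects (0.2-1.6 weeks of lag, 0.04-0.8 weeks of mean PFS) rest on assumed delay frequencies, delays spread evenly up to the cap, exponential progression and full adherence to the scan schedule. Delays bunched at the 3-week cap would give more; the safeguards above would give less. The direction for median PFS cannot be stated in advance, which is itself a reason to fix the scan dates.

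The six-month survival endpoint and the decision rules built on it do not depend on scans.

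**What to change.** Change the Phase II footnote in Section 7 to tumour imaging every 8 weeks (+/- 1 week) from one fixed date, regardless of cycle delays, until progression while on treatment. The date can be registration, where PFS starts, or Cycle 1 Day 1. Section 5 puts registration within 3 working days before treatment, so the choice matters little, but it should be stated.

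Change the Day 22 of Cycles 2, 4 and 6 grid entry to match. Amending the footnote alone would leave Phase II with the mismatch that Phase Ib has now.

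Counted from Cycle 1 Day 1, scans fall due on days 57, 113 and 169 (1 + 56, then + 56 each). The current undelayed days 50, 106 and 162 are each 7 days earlier, at the edge of the window, so subjects on schedule need no extra scans.

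The cost is occasionally one more scan for a delayed subject, and scans that may not coincide with a cycle visit. The change does not touch dosing or treatment rules. It also leaves the 3-monthly off-study interval as it is, so scans about 13 weeks apart remain possible for subjects who leave before progression.
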